### 3. Outcome

The primary outcomes included the corrected head circumference, weight, and height of the newborns at 1 month, 3 months, and 6 months of age. Additionally, parental anxiety and depression status was assessed using the Trait Anxiety Inventory (T-AI), which measures long-term and stable anxiety tendencies, and the State Anxiety Inventory (S-AI), which evaluates current or recent anxiety states. Parental self-efficacy and satisfaction with their parenting role were assessed using the Child-Parental Self-Competence Scale (C-PSOC).

Secondary outcomes included the length of hospital stay, discharge weight, and the number of unplanned hospitalizations.

Confounding factors included fetal gender, gestational age, birth weight, duration of oxygen therapy, duration of total enteral feeding, and the duration required to

transition from full enteral feeding to full oral feeding, defined as the time from the initiation of oral feeding (when preterm infants begin to suck voluntarily and consume the first milk volume exceeding 5 mL) to the complete establishment of full oral feeding.

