#### 4. Sample Size Calculation

With the assistance of Select Statistical Services (<https://select-statistics.co.uk/calculators/sample-size-calculator-two-means/>), the sample size was determined. This calculation utilizes the following formula to compute the sample size  $n$ :

[figure not shown]
$$n = \frac{2 \times (Z_{\alpha/2} + Z_{\beta})^2 \times \sigma^2}{d^2}$$

Among them, " $Z_{\alpha/2}$ " denotes the critical value of the standard normal distribution at  $\alpha/2$  (for a 95% confidence level,  $\alpha = 0.05$ , and the corresponding critical value is 1.96); " $Z_{\beta}$ " denotes the critical value of the standard normal distribution at  $\beta$  (for a statistical power of 80%,  $\beta = 0.2$ , and the corresponding critical value is 0.84); " $\sigma^2$ " represents the population variance, which is set at 2.5; and "d" refers to the minimum detectable difference, which is set at 1.5 for the primary outcome analysis. Based on these parameters, the required minimum sample size per group is calculated to be 18 participants.

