#### 5. Statistical Analysis

Measurement data that conformed to a normal distribution were expressed as mean  $\pm$  standard deviation (SD). Independent sample t-tests and paired sample t-tests were employed to assess intergroup statistical differences. For measurement data that did not conform to a normal distribution, results were summarized as median (interquartile range), and the Mann-Whitney U test was applied to evaluate statistical differences between groups. Categorical data were presented as frequency and percentage [n (%)] and analyzed using the chi-square test. Repeated measurement data were examined using repeated measures analysis of variance (ANOVA). All statistical analyses were conducted using SPSS version 25.0.

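### No baseline parental anxiety score is planned as a covariate: the T-AI, described as stable, is listed only as an outcome, with no timing given and no adjusted analysis of the S-AI

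*Combined protocol and SAP*

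**What the plan says.** In section 4.1, under 3. Outcome, the paragraph on primary outcomes covers infant growth at 1, 3 and 6 months and then adds the parental scales. For the parents' anxiety and depression it names the "Trait Anxiety Inventory (T-AI), which measures long-term and stable anxiety tendencies", and pairs this with "the State Anxiety Inventory (S-AI), which evaluates current or recent anxiety states". A parenting competence scale (C-PSOC) follows. The 1, 3 and 6 month times are attached to the growth measures; no time is given for any parental scale.

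The same section lists covariates of concern: "Confounding factors included fetal gender, gestational age, birth weight, duration of oxygen therapy, duration of total enteral feeding", and one further feeding duration. All six describe the infant. None is a parental score.

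Under 5. Statistical Analysis: "Independent sample t-tests and paired sample t-tests were employed to assess intergroup statistical differences". Mann-Whitney U is planned for non-normal data, chi-square for categorical data, and repeated measures ANOVA for repeated data. No test is assigned to a named outcome, and no ANCOVA or regression model appears.

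**The concern.** The plan itself separates a scale for stable tendencies from one for current state, then treats both only as outcomes. A stable trait is more natural as a baseline measure: taken before the intervention, it describes the parent and should help to predict later state anxiety.

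Two things are at stake. First, if the T-AI is measured only after the intervention, a difference between groups cannot be told apart from one that was there at the start. With small groups such gaps are not rare, and the readable text describes no allocation method that would limit them. Second, the S-AI comparison would carry the same starting gap and would forgo whatever precision a baseline anxiety score could supply.

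**Working it through.** **Inputs from the plan (4. Sample Size Calculation).** Two-sided alpha 0.05, "and the corresponding critical value is 1.96"; power 80%, value 0.84; variance 2.5; difference 1.5; 18 per group.

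**Inputs assumed.** The documents give no correlation r between baseline T-AI and follow-up S-AI, so I use 0 to 0.7. The variance and difference are tied to no named outcome; applying them to the S-AI is an assumption, as is one parental score per infant.

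**The plan's own figure.** n = 2 × (1.96 + 0.84)² × 2.5 / 1.5² = 17.42, rounded up to 18. It reproduces.

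**Unadjusted power.** Standardized difference = 1.5/√2.5 = 0.95. Noncentrality = 0.949 × √(18/2) = 2.85. A two-sided t-test on 34 degrees of freedom has power 79.0%.

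**Power with one baseline covariate.** ANCOVA multiplies the residual variance by 1 − r², so the standardized difference becomes 0.949/√(1 − r²), on 33 degrees of freedom. The last column repeats this for a smaller effect of 0.5 SD, where unadjusted power is 30.8%.

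| r (assumed) | 1 − r² | Power at 0.95 SD | Power at 0.5 SD |
|---|---|---|---|
| 0 | 1.00 | 78.9% | 30.8% |
| 0.2 | 0.96 | 80.5% | 31.8% |
| 0.3 | 0.91 | 82.5% | 33.3% |
| 0.4 | 0.84 | 85.4% | 35.6% |
| 0.7 | 0.51 | 97.2% | 53.2% |

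A useless covariate (r = 0) costs 0.1 percentage point, from 79.0% to 78.9%.

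**Does T-AI add to baseline S-AI?** Assume correlations with follow-up S-AI of 0.5 (baseline S-AI) and 0.4 (T-AI), and 0.7 between the two baseline scores. Baseline S-AI alone explains 0.5² = 0.25 of the variance: power 89.1%. Both together explain (0.25 + 0.16 − 2 × 0.5 × 0.4 × 0.7)/(1 − 0.49) = 0.255: power 89.2%. In this example T-AI adds almost nothing.

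**Chance imbalance.** The standard error of a baseline difference is √(2/18) = 0.33 SD. Even under random allocation, a gap of 0.5 SD or more in either direction is 0.5/0.333 = 1.5 standard errors, which occurs about 13% of the time (normal approximation).

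**Multiplicity.** With independent tests at 0.05, the chance of at least one false positive is 1 − 0.95^k. For the three parental scales it is 14.3%, against 9.8% without T-AI. Counting also nine growth tests (three measures at three times), it is 46.0% for 12 tests and 43.1% for 11. Independence is itself doubtful here, since T-AI and S-AI are expected to correlate.

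**The case against.** The strongest objection is that the plan's silence is being read as a choice. The Statistical Analysis section assigns no test to the S-AI. If the S-AI is taken before and after the intervention, the repeated measures rule would apply and each parent's earlier score would enter the analysis. This stands: one cannot say that the plan compares S-AI by an unadjusted t-test. It does not remove the point, because no baseline measurement is stated and no covariate is named. A before-and-after comparison is also not equivalent to ANCOVA. With equal variances, the variance factor for a change score is 2(1 − r), where r is the correlation between baseline and follow-up S-AI, against 1 − r² for ANCOVA: 1.00 against 0.75 at r = 0.5, and 0.60 against 0.51 at r = 0.7.

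A reader might also infer that the T-AI is close to a null test, that the plan wastes a known precision gain, or that including the T-AI materially inflates false positives. The documents do not support these readings:

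- The first rests on the description of the scale as stable. No expected T-AI effect and no duration of the intervention are given, and 2. Intervention and Control includes psychological counselling with outpatient and telephone follow-up. Power for a T-AI comparison runs from 5% to 79% as its true effect goes from nil to the full 0.95 SD.
- The second needs a timing and a correlation that the documents do not give.
- The third amounts to 2.9 percentage points (46.0% against 43.1%). The larger matter there is the absence of any multiplicity rule, which is a separate issue. The wording of the outcome paragraph also leaves it unclear whether the T-AI is primary at all.

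Finally, removing the T-AI from the outcomes altogether is partly a matter of preference; relabelling it also meets the concern.

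**Conclusion.** The point holds as a gap in design and analysis. A scale that the plan calls stable is listed as an outcome, neither anxiety scale has a stated assessment time, and no baseline parental anxiety score is used as a covariate in any listed method.

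The benefit of closing the gap ranges from slight to substantial: at 0.95 SD and 18 per group, from 79% power to 80.5% at r = 0.2 and to 97% at r = 0.7. That range rests on an assumed correlation and on planning values not linked to the S-AI. The gain may belong to baseline S-AI as much as to T-AI, and it concerns the parental scales; nothing in the documents suggests a gain for growth. The firmer argument is interpretation: without a baseline score, a pre-existing anxiety gap cannot be separated from an effect of care. This is a low-cost improvement, not a finding that the trial is invalid.

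**What to change.** - State when the T-AI and S-AI are given. Give the T-AI, and the S-AI if feasible, at enrolment before group assignment.
- Prespecify ANCOVA of follow-up S-AI on group, with the baseline anxiety score or scores as covariates, as the main S-AI analysis, and name the follow-up time.
- If the T-AI is also kept as a follow-up outcome, label it exploratory and adjust it for its own baseline.
- Much of the Outcome and Statistical Analysis text is in the past tense, so data may already be in hand. In that case report when the T-AI was taken, and use it as a covariate only if that was before the intervention.

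Cost: no new instrument and no extra participants; one added questionnaire sitting if a scale is given both at enrolment and at follow-up; one degree of freedom per covariate; a few lines in the plan. The sponsor gives up a confirmatory claim about trait anxiety. If the data are already collected without a baseline score, the adjustment cannot be recovered, and the S-AI and T-AI results should be reported with that limitation.

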### **Research Plan, Technical Approach, Organizational Structure**

#### **4.1 Research Plan**

##### 1. Inclusion and exclusion criteria

The inclusion criteria were as follows: gestational age ranging from 28 to 36 weeks, stable vital signs for at least 24 hours, and parental accompaniment of preterm infants during hospitalization. The exclusion criteria included: preterm infants with severe congenital or genetic disorders, dysfunction of vital organs, or requiring mechanical life support; preterm infants requiring surgical intervention; and preterm infants with a birth weight below 500 grams.

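### Length of stay is compared without adjustment across infants of 28 to 36 weeks' gestation, although the plan itself names gestational age as a confounding factor

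*Combined protocol and SAP*

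**What the plan says.** All of this stands in section 4.1 (Research Plan) of the combined protocol and SAP.

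- Item 1 (inclusion and exclusion criteria) admits infants with "gestational age ranging from 28 to 36 weeks, stable vital signs for at least 24 hours". It sets no limit on postnatal age at entry.
- Item 3 (outcome) states: "Secondary outcomes included the length of hospital stay". It gives no unit, no start (birth, admission or enrolment), no end and no discharge criteria.
- Item 3 then says: "Confounding factors included fetal gender, gestational age, birth weight, duration of oxygen therapy, duration of total enteral feeding", and adds the time taken to reach full oral feeding. It ties this list to no outcome and no model.
- Item 5 (statistical analysis) says, for normally distributed data, "Independent sample t-tests and paired sample t-tests were employed to assess intergroup statistical differences". For other continuous data, "the Mann-Whitney U test was applied to evaluate statistical differences between groups". The remaining methods are the chi-square test for categorical data and repeated measures ANOVA for repeated measurements. Neither fits a single duration per infant. No ANCOVA, regression or stratified comparison is named.
- The supplied text describes no stratified or matched allocation.

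**The concern.** Infants at the two ends of the entry window differ by 8 weeks, or 56 days, of maturity at birth. More immature infants can be expected to stay longer, and the plan acknowledges this by listing gestational age as a confounder. It then prescribes no analysis that uses the list.

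Two things follow. First, variation in stay that comes from maturity remains in the error term, so a real reduction in stay is harder to detect. Second, with small groups the arms may differ by chance in mean gestational age. An unadjusted comparison then carries that difference straight into the estimated effect on stay.

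The undefined start adds to this. If stay is counted from birth or admission, it includes days before the infant entered the trial, because entry depends on "stable vital signs for at least 24 hours" and not on age.

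**Working it through.** **The plan's own figure.** Item 4 gives α = 0.05 two-sided ("and the corresponding critical value is 1.96"), Z = 0.84 for 80% power, variance 2.5 and difference 1.5:

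n = 2 × (1.96 + 0.84)² × 2.5 / 1.5² = 39.2 / 2.25 = 17.42, rounded up to 18 per group.

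This reproduces. It is a minimum for the primary outcome and carries no information about length of stay. I use 18 per group below only as the stated size.

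**Assumptions.** The documents give no SD of stay, no distribution of gestational age and no relation between the two. I assume:

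- gestational-age SD of 1.0 to 2.31 weeks; the upper value is an even spread over the window, 8/√12 = 2.31 weeks;
- stay shorter by 0.5 to 1.0 day per extra day of gestation (the slope);
- residual SD of 5 to 14 days;
- a 7-day effect, for illustration.

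**Share of variance due to maturity.** Maturity SD = 7 × slope × gestational-age SD. Share = maturity SD² / (maturity SD² + residual SD²).

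- Even spread, slope 1, residual SD 10: maturity SD = 7 × 2.31 = 16.2 days; total SD = √(16.2² + 10²) = 19.0 days; share 72%.
- Lowest case (SD 1.0, slope 0.5, residual 14): maturity SD 3.5 days; 3.5² / (3.5² + 14²) = 6%.
- Highest case (SD 2.31, slope 1, residual 5): 16.2² / (16.2² + 5²) = 91%.

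**Detectable difference at 80% power.** 2.80 × SD × √(2/18) = 2.80 × SD / 3. In the even-spread case with residual SD 10, this is 2.80 × 19.0 / 3 = 17.7 days unadjusted and 2.80 × 10 / 3 = 9.3 days once gestational age is removed.

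**Power for 7 days** (noncentral t, 18 per group, residual SD 10):

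| Gestational-age SD (weeks) | Slope | Total SD (days) | Unadjusted | Adjusted |
|---|---|---|---|---|
| 1.0 | 0.5 | 10.6 | 49% | 53% |
| 1.5 | 0.7 | 12.4 | 38% | 53% |
| 2.31 | 0.7 | 15.1 | 27% | 53% |
| 2.31 | 1.0 | 19.0 | 19% | 53% |

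With residual SD varied over 7, 10 and 14 days, adjusted power exceeded unadjusted power in every case. The mildest gain was 29% to 31% (SD 1.0, slope 0.5, residual 14). The strongest was 21% to 83% (SD 2.31, slope 1, residual 7). These figures ignore the small loss from chance imbalance in the covariate; one or two degrees of freedom change them by less than one percentage point.

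**Chance imbalance.** Under simple random allocation (assumed), the SE of the difference in mean gestational age is SD × √(2/18) = SD / 3.

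- SD 2.31 weeks: SE 0.77 weeks (5.4 days); a gap of a week or more has probability about 19%.
- SD 1.5 weeks: SE 0.5 weeks (3.5 days); about 5%.
- SD 1.0 week: SE 0.33 weeks (2.3 days); about 0.3%.

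A one-week gap moves the unadjusted difference in stay by 7 days at slope 1 and by 3.5 days at slope 0.5.

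**Is a different endpoint needed?** Postmenstrual age at discharge is gestational age plus stay from birth. With gestational age in a linear model on the untransformed scale, adding it to the outcome changes only its own coefficient; the group coefficient is identical. Compared without adjustment, postmenstrual age has slope (1 − s) on gestational age, where s is the slope for stay. With SD 2.31 and residual 10, power is therefore equal for the two measures at s = 0.5 (35% each). At s = 0.4 postmenstrual age does worse, 31% against 40%.

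**The case against.** The strongest reply is that the plan does recognise maturity. Gestational age and birth weight are on its list of confounding factors, so a reader should not infer that they were overlooked. That stands. The defect is that the analysis section never uses the list.

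A reader might also infer that most of the spread in stay is maturity plus time before enrolment. The documents do not support this. Most holds for an even spread over the window and a steep slope, but the share is often below half with a narrower sample or a shallower slope. The exclusions for life support, organ dysfunction and surgery may thin the most immature end. The part before enrolment has no figure at all, and it disappears if stay is counted from enrolment, which the text leaves open.

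It is also fair to say that under random allocation chance imbalance is already reflected in the standard error, so the unadjusted test keeps its error rate. That limits the point to lost precision, and to an estimate that can mislead in the particular trial when the groups happen to differ. Systematic bias would need groups that differ systematically in gestation or time of entry, which the supplied text neither shows nor guards against.

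Finally, this is one of three secondary outcomes, and the stated sample size is for the primary outcome. Low power for stay is not an error in that calculation.

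**Conclusion.** The point holds as a moderate one. The plan names gestational age as a confounder, admits infants up to 8 weeks apart in gestation, and compares length of stay only by unadjusted tests. Adjustment raised power for a 7-day effect in every case tried. At residual SD 10 the contrast is 19% to 49% unadjusted against about 53% adjusted. The size depends on the assumed gestational-age SD, slope, residual SD and effect; none of these is in the documents, and the benefit may be small if the sample is narrow in gestation.

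Two stronger conclusions are not supported. That the outcome must be replaced by postmenstrual age at discharge does not follow, because covariate adjustment gives the same group estimate. That stay is definitely counted in days from birth is an inference, because no start or unit is given. The missing definition is itself the gap.

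**What to change.** 1. Keep length of stay as the outcome and state its unit, start and end, for example birth or enrolment to discharge.
2. Compare groups by a linear model with gestational age at birth as covariate, and add postnatal age at enrolment. On the untransformed scale, with both in the model, the group estimate is the same whether stay runs from birth or from enrolment. This does not extend to a count from hospital admission if age at admission varies.
3. If stay is skewed, use a log scale or robust or bootstrap standard errors. The equivalence in item 2 does not hold on a log scale, so the start must be fixed beforehand.
4. Do not adjust for the oxygen and feeding durations on the confounder list. They can arise after enrolment and may be affected by the intervention.
5. Postmenstrual age at discharge may be reported descriptively.

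The cost is a few sentences in the statistical analysis section and one or two degrees of freedom. Gestational age is already a named variable. No passage says that the date of enrolment is recorded, so that date should be added to data collection.

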##### 2. Intervention and Control

FICare nursing method guided by Swanson's caring theory encompasses the following five dimensions:

Understanding: A neonatologist provided a comprehensive explanation regarding the developmental progress of premature infants, potential complications, and essential aspects of nursing care to ensure the family gained a thorough understanding

of the care requirements for premature infants.

Accompaniment: Two nursing guides provided essential support to parents of newborns in the NICU, helping to alleviate the anxiety and sense of helplessness among family members and fostering a relationship of trust between the medical staff and the families.

Help: A neonatal nurse played a guiding role in facilitating parental involvement in the daily care of premature infants, which encompassed feeding guidance, introduction of complementary foods, skin care, and related aspects.

Empowerment: A psychological counselor was assigned to provide psychological counseling and guidance to new parents, offering appropriate emotional support and assisting them in accessing necessary social and professional resources.

Maintaining Confidence: A neonatologist and a nurse monitored neonatal development through outpatient visits and telephone follow-ups to encourage families to sustain their confidence in improving infant health outcomes and to support them in maintaining a positive outlook when facing challenges in caregiving.

The control group will continue to receive the traditional model of hospital care, encompassing standard medical services such as physical health monitoring and nutritional support.

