#### 4.2 Technical Approach

#### 4.3 Organizational mode

The project leader assumes responsibility for the planning, coordination, and supervision of the entire research process, including decision-making, resource allocation, and risk management. The research focuses on preterm infants, and the project leader is tasked with applying for research sites and securing necessary equipment support. Additionally, the leader collaborates with relevant departments and institutions to promote the implementation of family-participatory care based on Swanson's Caring Theory in the context of preterm infant care. Other project members are assigned specific responsibilities, such as data collection, care

intervention, and outcome analysis. Furthermore, the project's progress and outcomes are regularly evaluated and monitored. Based on these evaluations, the research plan and intervention strategies are adjusted in a timely manner to ensure the study's effectiveness and feasibility.

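### Sex, gestational age and birth weight are named as confounding factors, but the growth outcomes are compared with unadjusted tests only and the list is given no use

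*Combined protocol and SAP*

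**What the plan says.** Section 4.1, item 3 (Outcome), puts growth first: "The primary outcomes included the corrected head circumference, weight, and height of the newborns", measured at 1, 3 and 6 months. The same section then says: "Confounding factors included fetal gender, gestational age, birth weight, duration of oxygen therapy, duration of total enteral feeding". A sixth item, the time from first oral feeding to full oral feeding, closes the list. The list is not mentioned again anywhere in the document.

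Section 4.1, item 5 (Statistical Analysis), is the whole analysis plan. For normally distributed measurements, "Independent sample t-tests and paired sample t-tests were employed to assess intergroup statistical differences". Non-normal measurements go to the Mann-Whitney U test, categorical data to chi-square, and repeated measurements to repeated measures ANOVA. No covariate, regression, ANCOVA, mixed model, stratification or matching is named.

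Section 4.1, item 4 (Sample Size Calculation), sizes an unadjusted comparison of two means. The difference, "which is set at 1.5 for the primary outcome analysis", has no unit and no named outcome. With a variance of 2.5, "the required minimum sample size per group is calculated to be 18 participants".

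Item 1 admits infants of 28 to 36 weeks' gestation and sets only a lower birth-weight limit, 500 g.

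**The concern.** A plan that calls variables confounders is expected to say how it deals with them. Here the list stands in one section, and the methods in another have no place for it. The listed tests could compare the factors between groups, but such a comparison does not adjust the growth outcomes.

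What is at stake depends on allocation, which cannot be judged from the supplied text: front matter has been removed and nothing is shown under heading 4.2. Under random allocation, the unadjusted tests keep their error rate. What is lost is the precision that sex, gestational age and birth weight could buy in a group spanning eight weeks of gestation. Under non-random allocation, differences in these factors can bias the growth comparison.

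The list also mixes two kinds of variable. Sex, gestational age and birth weight are fixed before study care starts. The feeding durations and total oxygen duration may accrue after it starts. The intervention includes "facilitating parental involvement in the daily care of premature infants, which encompassed feeding guidance", so the feeding durations in particular may be affected by it. With no stated rule, an analyst could adjust for all six and remove part of the effect under study.

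**Working it through.** **Inputs from the plan (Sample Size Calculation):** two-sided alpha 0.05 (z = 1.96), power 80% (z = 0.84), variance 2.5, difference 1.5.

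**The plan's own figure.** 2 × (1.96 + 0.84)² × 2.5 / 1.5² = 17.42, rounded up to 18 per arm. This reproduces. The point does not depend on any error in the sample size.

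**Assumptions.** The difference and variance apply to a growth outcome at a single visit. R² is the share of outcome variance explained by gestational age, birth weight and sex together; it is not in the documents and is shown as a range.

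**Unadjusted t-test, 18 per arm.** SE = √(2.5 × 2/18) = 0.527; df = 34; noncentrality = 1.5/0.527 = 2.85. Noncentral-t power is 0.790. The 95% half-width is 2.032 × 0.527 = 1.07.

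**ANCOVA with three covariates, 18 per arm.** df = 2 × 18 − 2 − 3 = 31. The expected inflation for chance covariate imbalance is 1 + 3/(2 × 18 − 6) = 1.10. SE = √(2.5 × (1 − R²) × 2/18 × 1.10).

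| R² | SE | Power | Change from 0.790 |
|---|---|---|---|
| 0 | 0.553 | 0.748 | −0.042 |
| 0.05 | 0.539 | 0.769 | −0.021 |
| 0.1 | 0.524 | 0.791 | +0.001 |
| 0.2 | 0.494 | 0.836 | +0.046 |
| 0.4 | 0.428 | 0.924 | +0.134 |

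Power breaks even at R² = 0.096.

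**Interval width.** With a critical value of 2.040 on 31 df, the half-width is 1.01 at R² 0.2 and 0.87 at R² 0.4, against 1.07 unadjusted. The interval is therefore 6% and 18% narrower.

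**Check by simulation** (20,000 trials per setting, random allocation, two normal and one binary covariate, 18 per arm). Adjusted power was 0.752, 0.773, 0.793, 0.836 and 0.922 at the five R² values, in line with the table. At R² 0, 0.2 and 0.4, type I error was 0.051, 0.048 and 0.050 unadjusted, and 0.050, 0.049 and 0.050 adjusted. Both analyses are valid under random allocation; they differ in precision.

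No power is given for a mixed model over three visits, because the documents state no within-infant correlation.

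**The case against.** Several points on the other side have weight.

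- **The list may be meant for a table of group characteristics.** Chi-square needs a categorical variable, and sex is the only plainly categorical one in the Outcome section. This is plausible, but the plan does not say so, and such a table leaves growth unadjusted.
- **Corrected growth may already deal with gestational age.** If the undefined word means corrected age, it removes part of that dependence, and R² would be smaller and nearer break-even. It would not remove differences due to birth weight or sex.
- **Repeated measures ANOVA can take covariates.** It can, but none is specified.
- **Under random allocation nothing planned is invalid.** This stands: adjustment is then better practice, not the repair of an error. Chance imbalance is already inside the unadjusted standard error and should not be counted as a second harm.
- **The size rests on assumed R².** This also stands. At 18 per arm the result runs from a loss of 4 points to a gain of 13. Any larger arm size would be a further assumption.

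A reader might also infer that the model will be chosen after the results are seen, because section 4.3 (Organizational mode) says: "Based on these evaluations, the research plan and intervention strategies are adjusted in a timely manner". The documents do not support that. The section describes project management and mentions neither covariates nor review of outcomes by group. It is at most a reason to fix the covariate set early.

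**Conclusion.** The gap is real: three baseline variables are named as confounding factors, the growth outcomes are tested unadjusted, and no use is given for the list. It should be fixed, but it is not fatal.

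A reader might go further and conclude that the growth comparisons are biased. The supplied text does not support that, because the allocation method is not visible. Bias is possible if allocation is not random. If it is random, the cost is precision.

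Adjustment pays at 18 per arm if the three factors explain more than about 10% of outcome variance. At 20 to 40%, power rises from 79% to between 84% and 92%, and the interval narrows by 6 to 18%. Below about 10% there is a small loss, to 75% at worst. These figures hold for a single-visit ANCOVA and assume that the plan's difference and variance describe a growth outcome.

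**What to change.** In the Statistical Analysis section:

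1. Make the main growth analysis an ANCOVA, or a linear mixed model over 1, 3 and 6 months with group, visit and group-by-visit, adjusted for gestational age, birth weight and sex.
2. Fix this covariate set in writing before any outcome is compared by group.
3. Keep the unadjusted comparison as a sensitivity analysis.
4. Leave the two feeding durations and total oxygen duration out of the main model, and report them by group.
5. State how infants are allocated. If allocation is not random, add that adjustment reduces confounding but does not remove it.

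The cost is SAP wording and a standard SPSS procedure, on three variables the plan already lists. The downside is three degrees of freedom, and a small power loss if the factors explain less than about 10% of outcome variance at 18 per arm.
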